Pupil Dilation (may perform post-dilation eye exams in any order)	OU		OU		
Dilated Ophthalmoscopy	OU		OU		
Optic Disc Examination	OU		OU		
Determination of Eligibility	X		X	X	
Contact Interactive Response System ^m	X		X	X	
Treatment and/or Sham Administration				X	

IOP = intraocular pressure; OU = both eyes; SLT = selective laser trabeculoplasty; X = do procedure; Hour 0 = 08:00 ± 1 hour; Hour 2 = Hour 0 + 2 hours (± 30 min); Hour 8 = Hour 0 + 8 hours (± 30 min)

- ^a Washout may begin after all screening procedures have been completed and the Reading Center has confirmed central endothelial cell density.
- ^b Baseline visit procedures can be performed over a 3-day period. Perform pupil dilation/diagnostic procedures after the completion of the final IOP measurement or a different day. If, after initial washout, the investigator believes the IOP does not meet entry criteria due to inadequate washout and if time remains in the washout period, he/she may perform additional washout up to a total of 56 days.
- ^c If the patient reports symptoms or findings of concern in the Day 2 phone call (including but not limited to photophobia, blurred vision, eye pain, vitreous floaters), the investigator must bring the patient in for ophthalmic examination.
- ^d In countries/institutions where required by local institution or health authority, an additional serum test may be done any time between Baseline and Bimatoprost SR administration, with negative results for all tests confirmed prior to the time of Bimatoprost SR/sham injection. Pregnancy testing at Baseline is required regardless.
- ^e Blood and urine samples are collected only at Screening unless a retest is necessary.
- ^f The examination may also include, [REDACTED] See Procedure Manual for details.
- ^g Manifest refraction will be used to provide a correction for best-corrected visual acuity testing. At all study visits, if there is a 2-line or more reduction in visual acuity from the last best-corrected visual acuity performed, a repeat manifest refraction in both eyes and best-corrected visual acuity will be performed.
- ^h At selected sites/patients, additional IOP measurements will be performed at Hour 2 and Hour 8.

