A sustained-release (SR) formulation of bimatoprost was developed at Allergan, Inc. to evaluate ocular antihypertensive therapies that do not require patient self-administration. Bimatoprost SR refers to the biodegradable, sustained-release, preservative-free bimatoprost implant which is preloaded in an applicator for administration; together they comprise the Bimatoprost SR product. The Bimatoprost SR implant is injected into the AC via the corneal limbus using the prefilled applicator. The biodegradable polymer matrix gradually degrades to carbon dioxide and water so that there is no need to remove the Bimatoprost SR implant once the drug has been released. The Bimatoprost SR implant used in this study contains a total preservative-free bimatoprost load of 10 µg, and intracameral administration of this dose strength is expected to reduce the total daily drug exposure to the eye by approximately 126-fold compared with topical LUMIGAN 0.03% application over 4 months, as well as possibly reducing the adverse effects observed with topical glaucoma medications. The Bimatoprost SR implant is expected to release drug over approximately 4 months, and [REDACTED] polymer matrix degradation is expected within approximately 12 months. Although the biodegradation process of the Bimatoprost SR implant exceeds the drug release duration, experience from preclinical studies, the phase 1/2 (Study 192024-041D), and approved intravitreal implants composed of similar biodegradable polymers provide support for the anticipated safety in a phase 3 clinical trial with repeated administration.

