4.3 Inclusion Criteria

The following are requirements for entry into the study:

1. Male or female, 18 years of age or older

2. Written informed consent and authorization for use and release of personal health information are obtained in accordance with the relevant country and local privacy requirements, where applicable (eg, Written Authorization for Use and Release of Health and Research Study Information [United States (US) sites] and written Data Protection consent [European Union (EU) sites])
3. Patient is willing to withhold his/her IOP treatments according to the study requirements, and in the opinion of the investigator, can do so without significant risk. Note: If patients cannot discontinue their currently prescribed therapy for up to 8 weeks to meet the Washout period for study entry, the investigator may switch the patient's medication to one that requires a shorter washout interval during the washout of the original medication (see Section 8.2 and Table 7)
4. Patient has the ability to understand and the willingness to follow study instructions and requirements and is likely to complete all required visits and procedures
5. In the investigator's opinion, patient's IOP is not adequately managed with topical medication for reasons other than medication efficacy (eg, due to intolerance or nonadherence)
6. Negative pregnancy test at Baseline for females of childbearing potential

Ocular Inclusion Criteria for Both Eyes:

7. In the investigator's opinion, both eyes can be treated adequately with topical prostamide, prostaglandin, or prostaglandin analog (eg, LUMIGAN, Xalatan, Travatan) eye drops as the sole therapy if medication was taken as directed
8. In the investigator's opinion, patient's IOP can be adequately managed with SLT monotherapy
9. In the investigator's opinion, patient is a suitable candidate for SLT
10. Diagnosis of either OAG (ie, primary OAG, pseudoexfoliation glaucoma, pigmentary glaucoma) or OHT in each eye, requiring bilateral IOP-lowering treatment. (Note: diagnosis does not have to be the same in both eyes)
11. Central endothelial cell density by specular microscopy confirmed as being qualified by Reading Center assessment prior to beginning Washout
12. The iridocorneal angle must be independently confirmed as being qualified by 2 ophthalmologists using the following criteria:
 - a. Shaffer Grade ≥ 3 on clinical gonioscopy of the inferior angle

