4.4 Exclusion Criteria

The following are criteria for exclusion from participating in the study:

1. Uncontrolled systemic disease
2. Females who are pregnant, nursing, or planning a pregnancy, or who are of childbearing potential and not using a reliable means of contraception during the study (see Section 4.5.3)
3. Known allergy or sensitivity to the study medication or its components, any component of the delivery vehicle, or any diagnostic or surgical prep agents used during the study (eg, topical anesthetic, dilating drops, fluorescein, povidone-iodine)
4. Any condition which would preclude the patient's ability to comply with study requirements (including completion of the study)
5. Patients who have a condition or are in a situation, which, in the investigator's opinion, may put the patient at significant risk, may confound the study results, or may interfere significantly with the patient's participation in the study
6. Concurrent or anticipated enrollment in an investigational drug or device study or participation in such a study from 2 months prior to the Baseline visit through the final study visit
7. Previous use of commercially available Bimatoprost SR; concurrent enrollment in another Allergan Bimatoprost SR study; or previous enrollment in which an implant was received. Patients enrolled in the 192024-091/092 studies who were randomized to the control treatment and never received an implant may be considered for enrollment at the investigator's discretion.
8. Known history of bleeding disorder or prolonged bleeding after surgery (in the opinion of the investigator). Note: Patients receiving pharmacologic blood thinners (eg, aspirin, Coumadin) may be enrolled at the investigator's discretion.

Ocular Exclusion Criteria for Both Eyes:

9. History of previous laser trabeculoplasty
10. History or evidence of clinically relevant, substantial ocular trauma (eg, a traumatic cataract, traumatic angle recession, etc)
11. The following surgical history:
 - a. History or evidence of complicated cataract surgery: eg, surgery resulting in complicated lens placement (such as anterior chamber intraocular lens implant [IOL], sulcus IOL, aphakia, etc) or intraoperative complications (such as a posterior capsular tear [with or without vitreous loss], substantial iris trauma, etc).

Note: history of uncomplicated cataract surgery is not an exclusion.
 - b. History of phakic IOL insertion for refractive error correction

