For purposes of this study, females will be considered of childbearing potential unless they are naturally postmenopausal or permanently sterilized (ie, hysterectomy). Natural menopause is defined as the permanent cessation of menstrual periods, determined retrospectively after a woman has experienced 12 months of amenorrhea without any other obvious pathological or physiological cause. For women of childbearing potential who may participate in the study, the following methods of contraception, if properly used, are generally considered reliable: hormonal contraceptives (ie, oral, patch, injection, implant), male condom with intravaginal spermicide, diaphragm or cervical cap with spermicide, vaginal contraceptive ring, intrauterine device, surgical sterilization (bilateral tubal ligation, bilateral salpingectomy), vasectomized partner, or true sexual abstinence (when this is in line with the preferred and usual lifestyle of the subject).

The investigator and each patient will determine the appropriate method of contraception for the patient during the participation in the study.

If a female becomes pregnant during the study, the investigator will notify Allergan immediately after the pregnancy is confirmed and the patient will be exited from the study after appropriate safety follow up. The investigator will (1) notify the patient's physician that the patient was being treated with an investigational drug (and unmask the study treatment as needed for pregnancy monitoring), and (2) follow the progress of the pregnancy. The investigator must document the outcome of the pregnancy and provide a copy of the documentation to Allergan.

5. Study Treatments

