5.9.1.5 Retreatment with Bimatoprost SR

For all patients who meet retreatment criteria at Week 16, Cycle 2 Bimatoprost SR administration will occur at Week 16.

For patients who do not meet retreatment criteria at Week 16, Cycle 2 Bimatoprost SR administration may occur at the investigator's discretion during an unscheduled visit after Week 16 and prior to the Month 12 visit based on the investigator's clinical judgment regarding the patient's IOP control and if the retreatment criteria are met. Note: beyond Week 16, Cycle 2 administration is not mandatory even if the retreatment criteria are met.

Patients who have received nonstudy IOP-lowering treatment (prohibited during the study except for pre- and post-SLT administration, Section 4.5.1) in only 1 eye will still attend administration visits regardless of whether the eye receiving additional medication is the Bimatoprost SR eye or the SLT eye. If the eye treated with additional nonstudy IOP lowering medication is the Bimatoprost SR eye, the eye will receive Sham Bimatoprost SR administrations at the administration visits. If the eye treated with additional nonstudy IOP lowering medication is the SLT eye, that eye will continue to receive Sham Bimatoprost SR administrations. Patients who have been treated with nonstudy IOP-lowering medication in both eyes will not attend the administration day visits, nor will they attend the Day 2, Day 4 (phone call), and Week 2 (phone call) visits following an administration. Patients who have received nonstudy IOP-lowering medication in one or both eyes will be followed for the duration of the study through the Month 24/Exit visit.

Retreatment of an eligible implanted eye is permitted if the following criteria are met in that eye:

- IOP > 17 mm Hg
- There is no evidence of any of the following:

- Significant corneal findings related to presence of the implant (including corneal edema, peripherally adjacent to the implant location and/or central) at any visit
- Endothelial cell density less than 1800 cells/mm² by specular microscopy, confirmed at 2 consecutive visits on separate days
- Persistent and progressive corneal endothelial cell density decrease $\geq 15\%$ from baseline confirmed at 2 consecutive visits on separate days (scheduled or unscheduled)

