8.4.3.7 Bimatoprost SR Cycle 2 Day 1 Administration

The following procedures are performed at Week 16 (-2/+4 days) for all patients who meet retreatment criteria.

Patients who do not receive Cycle 2 administration at Week 16 will not attend the Cycle 2 Administration Day visit on Week 16, or the Day 2 Safety or Day 4 and Week 2 phone calls associated with administration at Week 16. For those patients not meeting retreatment criteria at Week 16, Cycle 2 may be performed at the investigator's discretion during an unscheduled visit after Week 16 and prior to the Month 12 visit if the retreatment criteria are met; in this case, inadequate control of IOP should be confirmed at another scheduled or unscheduled visit prior to initiation of Cycle 2. For patients who begin Cycle 2 after Week 16 and before Month 12, the Cycle 2 visits (Administration Day, Day 2 Safety Visit, and Day 4 and Week 2 Phone Calls) will apply at the time that Cycle 2 occurs. Regardless of the timing of Cycle 2, all regularly scheduled visits should be completed. Cycle 2 should be scheduled such that the Administration Day and the Day 2 Safety Visit do not occur on the day of a regularly scheduled study visit. However, if the Cycle 2 Day 4 or Week 2 Phone Calls overlap with a regularly scheduled visit, perform the regularly scheduled visit.

- Collection of adverse events
- Collection of concomitant medications and procedures
- Vital signs (at rest ≥ 5 minutes)
- Contact interactive response system for kit allocation (this contact may take place 1 day prior to the Cycle 2 administration day, if needed)
- Administer assigned study treatment
- Contact interactive response system to confirm kit assignment if applicable

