Patients who receive the second administration of Bimatoprost SR at Week 16 and patients who never receive a second administration may, at the investigator's discretion, skip the visits at Months 13, 15 and 22 if the patient has received nonstudy IOP lowering medication in both eyes; has $\leq 25\%$ of each implant remaining in the eye; and in the investigator's clinical judgment, has no safety or other concern that would require the patient to attend these visits. Please note: as described in Section 4.5.2, each eye should be evaluated on an individual basis when determining the need for additional nonstudy IOP-lowering treatments; initiation of treatment in one eye should not automatically lead to initiation of treatment in the contralateral eye.

- Collection of adverse events
- Collection of concomitant medications and procedures
- Vital signs (at rest ≥ 5 minutes)
- Pregnancy test for females of childbearing potential (as defined in Section 4.5.3) (Month 24/Exit only)

The following procedures should be performed in both eyes (procedures in bold should be done in the order shown):

- **Pre-Hour 0 examinations** (may perform in any order before Hour 0 IOP):
 - Macroscopic conjunctival hyperemia assessment (The examination will also include [REDACTED]
[REDACTED]
[REDACTED] may be performed at interim visits for appearance of or increase/decrease in hyperemia.)
 - Best-corrected visual acuity
- **Intraocular pressure measurement at Hour 0**
- **Non-contact examinations:** The following may be performed in any order, at any time before gonioscopy (including prior to Hour 0 IOP):
 - Macroscopic iris color assessment (Week 52 and Months 18 and 24/Exit only)
 - Manifest refraction (Week 52 and Months 18 and 24/Exit only)

- Visual field (If dilation is required to perform this test, then the visual field test should be performed after the last IOP measurement of the day.) (Week 52 and Months 18 and 24/Exit only)
- Specular microscopy (Weeks 40 and 52 and Months 16, 20, and 24/Exit only)
- [REDACTED] (at Week 52 and Month 24/Exit at selected sites in both eyes of all consenting patients who underwent assessment at Screening; may be done at interim visits at the discretion of the investigator. Perform any contact assessments following IOP measurements.)
- Biomicroscopy (The examination will also include, [REDACTED]
[REDACTED]
[REDACTED] may be performed at interim visits for appearance of or increase/decrease in hyperemia.)

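### No pregnancy test is scheduled before the second implant, although a negative test is required 4 to 9 days before the first

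*Protocol*

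**What the plan says.** Pregnancy testing appears at two scheduled timepoints in the protocol.

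- **Entry.** Section 4.3, criterion 6, asks for a "Negative pregnancy test at Baseline for females of childbearing potential". The test is in Table 2 and Section 8.4.2, and Table 2 footnote d adds: "Pregnancy testing at Baseline is required regardless".
- **Exit.** Section 8.4.3.11 and Table 6 place the second test at the final visit: "Pregnancy test for females of childbearing potential (as defined in Section 4.5.3) (Month 24/Exit only".

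The second implant is governed elsewhere. Section 8.4.3.7 opens with "The following procedures are performed at Week 16 (-2/+4 days) for all patients who meet retreatment criteria". It then lists adverse events, concomitant medications, vital signs, response-system contacts and treatment. Section 5.9.1.5 says "Retreatment of an eligible implanted eye is permitted if the following criteria are met in that eye". The criteria that follow cover IOP, corneal findings, endothelial cell density, remaining implant, inflammation and the investigator's view of safety for the eye. Neither section mentions pregnancy, and Table 4 and SAP Table 4-5 have no pregnancy-test row.

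Other controls exist. Section 4.4, exclusion 2, rules out women who are pregnant, nursing or planning a pregnancy, "or who are of childbearing potential and not using a reliable means of contraception during the study". Under Section 4.5.3, once a pregnancy is confirmed, "the patient will be exited from the study after appropriate safety follow up".

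**The concern.** The plan treats pregnancy as a bar to entry and a reason to exit. Before the first implant it does not rely on contraception alone: it also requires a negative test. It gives no reason for a lower standard when the same drug is implanted a second time.

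An implant cannot be stopped the way drops can. Section 1.2 states: "The Bimatoprost SR implant is expected to release drug over approximately 4 months". It expects polymer degradation to take about 12 months, and Section 4.5.1 describes removal as an unlikely event reserved for significant safety reasons. The moment before administration is therefore the last point at which exposure from the second implant is easily avoided.

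At stake is a pregnancy that nobody has yet recognised on the Cycle 2 administration day. A recognised pregnancy is already dealt with by Section 4.5.3.

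**Working it through.** The plan states no interval to reproduce, so the check is visit-day arithmetic.

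**Inputs**

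- Baseline is Day -3 to Day -1 (Section 4.3, criterion 15), counted with no Day 0.
- The first implant is on Day 4 with a +3 day window (Table 3), so Day 4 to Day 7.
- The second implant is at Week 16, -2/+4 days (Section 8.4.3.7), or later at an unscheduled visit before the Month 12 visit. The schedule has no separate Month 12 visit, so it is taken as Week 52, ±4 days (Table 5).
- The exit test is at Month 24, ±7 days (Table 6).
- SAP Table 17-2 counts target days from the first implant: Week 4 = 25, Week 52 = 361, Month 24 = 717. With that implant on study Day 4, study day = target + 3, giving Days 28, 364 and 720. All 13 targets from Week 4 to Week 52 equal 7 × week − 3, so week *w* is study Day 7*w* and Week 16 is Day 112.

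**From the Baseline test to each implant:** gap = (implant day − 1) + |baseline day|

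| Implant | Shortest | Longest |
|---|---|---|
| First, Day 4 to 7 | 3 + 1 = 4 days | 6 + 3 = 9 days |
| Second at Week 16, Day 110 to 116 | 109 + 1 = 110 days | 115 + 3 = 118 days |
| Second, day before an on-target Week 52 visit, Day 363 | 362 + 1 = 363 days | 362 + 3 = 365 days |
| Second, day before a Week 52 visit at +4, Day 367 | – | 366 + 3 = 369 days |

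**From the second implant to the next scheduled test (Day 720, range 713 to 727)**

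- After Week 16: 720 − 112 = 608 days, with range 713 − 116 = 597 to 727 − 110 = 617.
- After the latest flexible implant: 720 − 363 = 357 days, with minimum 713 − 367 = 346.

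Even the minimum of 346 days exceeds an assumed pregnancy of about 280 days. Unless the patient leaves early and has the exit procedures then (Section 8.9), no scheduled test could find a pregnancy that was present at the second implant.

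**Sensitivity to the day convention.** The protocol gives no study day for Week 16. Setting it at Day 113 gives 111 to 119 days. Counting it from an implant given on Day 4 to 7 gives 110 to 121 days. The differences are 1 to 3 days and do not matter.

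**Does Section 6.3.2 already cover it?** It says urine tests are done at the specified timepoints, and none is specified for Cycle 2. It requires that test results be confirmed negative before administration, but before the second implant the only scheduled result is the Baseline one. The extra serum test applies only where local rules require it, and Table 2 footnote d ties it to the period after Baseline. Section 6.3.2 therefore creates no test before the second implant.

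**The case against.** The strongest reply is that the plan tests at entry and then relies on contraception, and does so consistently. The first implant also releases drug for about 4 months with no test in that time. A pregnancy unrecognised at Week 16 would usually have begun during that release, so a Cycle 2 test would prevent added exposure and not first exposure. That is fair for a Week 16 implant. It is weaker for a late flexible one: taking 4 months as about 120 days, release from a Day 4 implant ends near Day 124, while a second implant can be given as late as Day 363 to 367.

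Other points also stand:

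- Adverse events and medications are queried at every visit, extra examinations are allowed (Section 8.7), and patients who leave early have the exit test. A pregnancy could therefore come to light without a scheduled test before Cycle 2.
- The stakes look low. In dogs, systemic levels were below quantitation at doses up to 60 µg, six times the 10 µg Stage 2 dose (60/10). Section 1.1 says most OAG/OHT patients are elderly.
- Section 6.3.2 puts no explicit limit to Cycle 1 on its sentence about negative results, so a site might read it as covering each administration.
- Table 4 footnote j is redacted and the Procedure Manual is not available here.

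None of this supplies a test before the second implant in the text that can be read. Low exposure and an older population did not lead the sponsor to waive the Baseline test, and enrolment is open from age 18.

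**Conclusion.** The concern holds. Followed as written, the plan gives a second implant 110 to 118 days after the last pregnancy test, or up to about 365 days after it (369 at the outer visit window), against 4 to 9 days for the first implant.

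The gap is narrow: it concerns a pregnancy not yet recognised on the administration day. The number of women of childbearing potential is not stated and is probably small. The documents quantify no fetal risk, so this is a missed inexpensive precaution and not a demonstrated harm. It has no bearing on the estimand, power or type I error. The change should be made, but the trial's conclusions do not depend on it.

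The conclusion rests on the readable text, on Week 52 serving as the Month 12 visit, on the SAP's day convention, and on an assumed pregnancy length of about 280 days.

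**What to change.** For females of childbearing potential, require a negative urine pregnancy test before Cycle 2 administration, whether at Week 16 or at the later unscheduled visit.

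- Add a pregnancy-test row to Protocol Table 4 and SAP Table 4-5.
- Add one line to Section 8.4.3.7.
- Add a criterion to Section 5.9.1.5: not pregnant, shown by a negative urine test.

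Done on the administration day, this cuts the interval from last test to second implant to 0 days. The cost is one site dipstick per eligible woman at a visit that already occurs, using kits the sponsor already supplies (Section 6.4). SAP Section 11.3.1 neither analyses nor lists pregnancy test results, so no analysis changes.
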